7.2 Definition of a Serious Adverse Event

In this study, a *serious adverse event* is defined as an AE that meets any of the following criteria:

- Results in death
- Is life-threatening
- The term *life-threatening* in the definition of an SAE refers to an event in which the subject was at risk of death at the time of the event. The term *life-threatening* does not refer to an event that hypothetically might have caused death if it were more severe.
- Requires hospitalization or a prolongation of an existing hospitalization
- In general, hospitalization signifies that the subject has been detained at the hospital or emergency ward for observation or treatment that would not have been appropriate in the physician's office or out-patient setting. Complications that occur during hospitalization are AEs, but not necessarily SAEs. An occurrence or complication that prolongs hospitalization is an SAE. When there is doubt as to whether hospitalization occurred or was necessary, the AE should be considered an SAE. Hospitalization for elective treatments of a preexisting condition that did not worsen from its original baseline level is not considered an SAE.

- A persistent or significant incapacity or substantial disruption of the ability to conduct normal life functions
- This definition is not intended to include AEs of relatively minor medical significance such as uncomplicated headache, nausea, vomiting, diarrhea, influenza and accidental trauma (e.g., sprained ankle) that may interfere or prevent everyday life functions but do not constitute a substantial disruption.
- Another important medical event
- Medical or scientific judgment should be exercised when deciding whether reporting is appropriate for other important medical events that may not result in death, be life-threatening, or require hospitalization but still may jeopardize the subject or may require medical intervention to prevent one of the outcomes listed in this definition. These events should also be considered serious. Examples of such events are intensive treatment in an emergency room or at home for allergic bronchospasm, blood dyscrasias, or convulsions that do not result in hospitalization.

An SAE requires additional detailed reports and follow-up. The content of these detailed reports must address the investigator's estimate of causality. The medical monitor will review the SAE to determine if it is an expected SAE (i.e., whether or not the SAE is identified in nature, severity, and frequency in the VP-102 Investigator's Brochure).

7.3 Recording Adverse Events and Serious Adverse Events

When an AE or SAE occurs, the investigator is responsible for reviewing all documentation (e.g., hospital progress notes, laboratory, and diagnostic reports, etc.) relative to the event(s). The investigator will record all relevant information about any AE (including SAEs) on the AE page of the eCRF. It is not acceptable for the investigator to send photocopies of the subject's medical records in lieu of the properly completed AE or SAE pages of the eCRF. These documents should not be sent unless they are specifically requested by the designated Medical Monitor. If this request occurs, all subject identifiers and protected health information should be blinded on the copies of the medical records before submission to the Sponsor and to the appropriate authorities.

The investigator will also attempt to report a diagnosis, instead of signs, symptoms, or other clinical information, for the AE. The diagnosis, not the individual signs and symptoms, should be documented on the appropriate page of the eCRF as the AE or SAE. In addition, SAEs need to be reported in the SAE report. AEs being processed as SAEs will also require additional documentation.

7.4 Assessment of Intensity

The investigator will assess the intensity for each AE and SAE reported during the study. The assessment will be based on the investigator's clinical judgment.

The classifications in Table 3 should be used in assigning intensity of each AE recorded in the eCRF.

Table 3 Classification of AEs by Intensity

Intensity	Definition
Mild AE	An event that is easily tolerated by the subject, causing minimal discomfort and not interfering with everyday activities
Moderate AE	An event that is sufficiently discomforting to the extent of interfering with normal everyday activities
Severe AE	An event that prevents the subject from performing normal everyday activities

AE: adverse event.

Any AE that changes in intensity during its course will be recorded in the eCRF at the highest level experienced by the subject.

An AE that is assessed as severe should not be confused with an SAE. Severity is a category used for rating the intensity of an AE (such as mild, moderate, or severe myocardial infarction). However, the event itself may be of relatively minor medical significance, such as a severe headache. Both AEs and SAEs can be assessed as severe. An AE is considered serious (an SAE) when it meets one of the predefined outcomes described in Section 7.2.

Local Skin Reactions should be rated based on the severity ratings in the Local Skin Reaction Guide that is provided.

7.5 Assessment of Causality

The investigator must estimate the relationship between the investigational product and the occurrence of each AE or SAE by using his or her best clinical judgment. Elements to consider for this estimate include the history of the underlying disease, concomitant therapy, other risk factors, and the temporal relationship of the event to the investigational product. The investigator will also consult the Investigator's Brochure or product label for marketed products in estimating the relationship.

Because of reporting timelines, the investigator might have minimal information to include in the initial SAE report. However, the investigator must always make an assessment of causality for every SAE before the transmission of the SAE report. The investigator may change his or her opinion of the causality in light of follow-up information, with subsequent amendment of the SAE report. Causality assessment is one of the criteria used to determine regulatory reporting requirements and should not be left blank in the SAE report. The same applies to AEs that are to be processed as SAEs. Some definitions to use in the assessment are provided in Table 4.

Table 4 Assessment of Causality of AEs

Term	Definition
Definitely related	The AE is clearly related to the investigational agent(s) or research intervention: the AE has a temporal relationship to the administration of the investigational agent(s) or research intervention and follows a known pattern of response, and no alternative cause is present.
Possibly related	The AE may be related to the investigational agent(s) or intervention: the AE has a temporal relationship to the administration of the investigational agent(s) or research intervention and follows a suspected pattern of response, but an alternative cause is present.
Probably related	The AE is likely related to the investigational agent(s) or intervention: the AE has a temporal relationship to the administration of the investigational agent(s) or research intervention and follows a known or suspected pattern of response, but an alternative cause may be present.
Unrelated (or not related)	The AE is clearly not related to the investigational agent(s) or intervention: the AE has no temporal relationship to the administration of the investigational agent(s) or research intervention, and follows no known or suspected pattern of response, and an alternative cause is present.

AE: adverse event.

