10.2. Adverse Events

Adverse events summaries will only consider TEAEs. TEAEs are defined as those adverse events that occurred after dosing and those existing adverse events that worsened during the study. If it cannot be determined whether the adverse event is treatment emergent due to an incomplete (partial) onset date, the adverse event will be considered to be treatment emergent. Adverse events with an onset day after the EOS visit will be included in listings but not considered TEAEs; therefore, such adverse events will not be considered for table summaries. Verbatim terms entered into the clinical database via the EDC system will be mapped to preferred terms and system organ classes using version 20.0 of Medical Dictionary for Regulatory Activities (MedDRA).

Each adverse event summary will be displayed by treatment group. Summaries that are displayed by system organ class and preferred terms will be ordered by descending order of incidence of system organ class and preferred term within each system organ class. Summaries of the following types will be presented:

- Overall summary of the TEAEs which contain an overview of each item below.
- Subject count and incidence rate of TEAEs by MedDRA system organ class and preferred term.
- Subject count and incidence rate of TEAEs by MedDRA preferred term and highest severity. At each level of subject summarization, a subject is classified according to the highest severity if the subject reported one or more events.
- Subject count and incidence rate of TEAEs by MedDRA preferred term and closest relationship to study drug (Related/Not Related). Related AEs are those reported as “Definitely”, “Probable” or “Possibly”. At each level of subject summarization, a subject is classified according to the closest relationship if the subject reported one or more events. Adverse events with missing relationship will be considered related for this summary.
- Subject count and incidence rate of Serious TEAEs by MedDRA system organ class and preferred term.
- Subject count and incidence rate of TEAEs leading to withdrawal of study medication by MedDRA system organ class and preferred term.

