10.3. Targeted Adverse Events- Local Skin Reactions

Local skin reactions (LSRs) to treatment reported by investigators and subjects will be recorded as adverse events. Two questions on the adverse event form are “Is this Adverse Event at a location where study drug was administered?” and “Did event occur during the paring procedure?” If the answer is Yes to the location question and No to the

paring procedure question, the adverse event will be considered a Local Skin Reaction. LSRs will be coded and summarized using similar methods as described in Section 10.2 for adverse events.

Summaries of LSRs will include the following:

- Subject count and incidence rate of LSRs by MedDRA system organ class and preferred term.
- Subject count and incidence rate of LSRs by MedDRA preferred term and highest severity. At each level of subject summarization, a subject is classified according to the highest severity if the subject reported one or more events.
- Subject count and incidence rate of LSRs by MedDRA preferred term and closest relationship to study drug (Related/Not Related). Related LSRs are those reported as “Definitely”, “Probably” or “Possibly”. At each level of subject summarization, a subject is classified according to the closest relationship if the subject reported one or more events. LSRs with missing relationship will be considered related for this summary.
- Subject count and incidence rate of serious LSRs by MedDRA system organ class and preferred term.
- Subject count and incidence rate of LSRs by study specific LSR categories. Mapping of LSRs will be done via a medical review. Possible categories of LSRs will include the following: Blistering, Pain, Pruritus, Erythema, Edema, Erosion/Ulceration, Flaking/Scaling/Dryness, Scabbing/Crusting, Pigmentation Changes.

Adverse events that appear at a location where drug was administered and occur during the paring procedure will not be considered LSRs. A separate summary table will be generated to summarize those adverse events that meet these conditions (i.e., the answer is Yes to the location question and Yes to the paring procedure question, therefore the adverse event will be considered as related to the paring procedure and not an LSR).

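### Table 4 rates causality against drug or research intervention while the SAP tabulates relationship to study drug, and it has no category for some events close in time to dosing, so drug-related AE incidence may be overstated for individual terms

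*Protocol*

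**What the plan says.** The text of Protocol 7.5 sets the target: "The investigator must estimate the relationship between the investigational product and the occurrence of each AE or SAE", using clinical judgment. Protocol 4.3.1 agrees, since both the AE listing and the eCRF carry relationship to the study drug.

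Table 4 in the same section supplies the definitions, and all four refer to the agent or an intervention. *Definitely related* begins "The AE is clearly related to the investigational agent(s) or research intervention". *Unrelated* joins three conditions: "the AE has no temporal relationship to the administration of the investigational agent(s) or research intervention", and the event "follows no known or suspected pattern of response, and an alternative cause is present". *Possibly related* needs a temporal relationship and an event that "follows a suspected pattern of response, but an alternative cause is present".

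SAP 10.2 summarises TEAEs by preferred term and "closest relationship to study drug (Related/Not Related). Related AEs are those reported as" definitely, probably or possibly related. It counts a missing relationship as related.

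SAP 10.3 says: "Adverse events that appear at a location where drug was administered and occur during the paring procedure will not be considered LSRs". It treats these events as related to paring and gives them a separate summary table. It does not say whether they leave the SAP 10.2 relationship table or are re-rated there.

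**The concern.** The definitions and the table built from them do not measure the same thing. Cohort 2 includes a procedure with its own risk of injury: paring with a scalpel or blade when thick scale is present, to be stopped on punctate bleeding or significant pain (Protocol 4.1). Protocol 7.1 accepts that protocol-mandated procedures can produce AEs. An investigator who applies Table 4 as written would rate a paring injury as related, and the SAP would present it as related to study drug.

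The second problem is that *Unrelated* requires the absence of a temporal relationship. A coincident illness or injury soon after an application may have no natural place in the scale.

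Safety and tolerability are a primary objective, and there is no control group against which a biased attribution would show.

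**Working it through.** The documents state no expected or target drug-related AE rate, so there is no figure to reproduce. The check is of the definitions, followed by an illustration of how far a misrating could carry.

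**Step 1: path of a paring injury.** Take a cut during paring at Treatment Visit 2, 3 or 4.
- It follows the first dose, so it is treatment emergent under SAP 10.2. At Treatment Visit 1 paring precedes the first application, so that visit is not at issue.
- If paring counts as a research intervention, the event has a temporal relationship, a known pattern and no other cause. Table 4 gives *Definitely related*.
- SAP 10.2 counts it as Related to study drug.
- SAP 10.3 excludes it from the LSR tables and lists it as related to paring.

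The same event can thus be related to paring in one table and to study drug in another.

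**Step 2: coverage of Table 4.** Table 4 uses three features: temporal relationship (2 levels), response pattern (3 levels) and alternative cause (2 levels), so 2 × 3 × 2 = 12 combinations. *Probably related* says an alternative cause may be present, which is read here as met either way.

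| Temporal | Pattern | Alternative cause | Category that fits |
|---|---|---|---|
| yes | known | no | Definitely, Probably |
| yes | known | yes | Probably |
| yes | suspected | no | Probably |
| yes | suspected | yes | Possibly, Probably |
| yes | none | no | none |
| yes | none | yes | none |
| no | known or suspected | yes or no (4 combinations) | none |
| no | none | no | none |
| no | none | yes | Unrelated |

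*Unrelated* fits 1 of 12 combinations and none of the 6 temporal ones. A related category fits 4 of those 6; the other 2 fit nothing. In all, 2 + 4 + 1 = 7 combinations fit no category and 2 fit two categories. A coincident event after dosing therefore falls into a gap. It becomes related by rule only if the field is left blank.

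**Step 3: how far misrating could move the rates (illustration).** Let p be the true share of subjects with at least one drug-related TEAE, and q the share of the remaining subjects wrongly counted as related. The inflation is q(1 − p). Both are assumptions. The value 29/33 = 88% is the any-AE rate in the earlier open-label VP-102 molluscum study (Protocol 2.2.2): a different disease, and not a drug-related rate.

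| p | q = 10% | q = 25% | q = 50% | q = 100% |
|---|---|---|---|---|
| 50% | 5.0 | 12.5 | 25.0 | 50.0 |
| 88% (29/33) | 1.2 | 3.0 | 6.1 | 12.1 |
| 95% | 0.5 | 1.3 | 2.5 | 5.0 |

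Entries are percentage points; at q = 0 the inflation is zero. When p is high, the any-related rate has little room to move. For a preferred term that the drug itself seldom causes, p is near 0 and the inflation is close to q. With about 35 subjects, each misrated subject adds 1/35 = 2.9 points to that term, because a subject is classified by the closest relationship reported.

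**The case against.** The strongest reply is that the governing instruction is sound. Protocol 7.5 directs the rating at the product by clinical judgment and offers Table 4 only as helpful definitions, and Protocol 4.3.1 says the eCRF records relationship to the study drug. An investigator following those sentences would not attribute a paring cut to VP-102. This stands, and it is why the documents support a risk of misclassification and not a demonstrated bias.

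Paring is also partly handled: the AE form asks about it, and a separate table shows the events. That helps a reader but leaves the SAP 10.2 relationship table unaddressed. Research intervention is undefined, so placing paring under it is a literal reading, though a natural one.

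A reader might infer that Table 4 pushes every event close in time to dosing into related. It does not: such an event with no response pattern fits no category and is left to judgment. Temporal relationship is undefined and need not mean mere closeness in time. Blanks should be few, since Protocol 9.1 has the monitor check that eCRF data are complete. However, the instruction in 7.5 against a blank causality field covers SAE reports and AEs processed as SAEs, not ordinary AEs.

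Occlusive tape is a weaker example than paring. Drug and tape are applied as one regimen, so their local effects are hard to separate, and the point does not rest on them.

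**Conclusion.** The misalignment is real and should be corrected. Table 4 rates against drug or intervention, the text of 7.5 and 4.3.1 ask about the drug, and SAP 10.2 labels the result as relationship to study drug. Table 4 also leaves events with a temporal relationship but no response pattern without a category, and the SAP counts a blank as related.

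The consequence is that drug-related incidence may be overstated, chiefly for terms such as bleeding or laceration. The any-related subject rate would probably change little, on the assumption that most subjects have a drug-related local skin reaction.

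Two stronger conclusions might be drawn, and the documents support neither. One is that the rate is overstated as a matter of fact; that would require investigators to follow Table 4 over the instruction that introduces it. The other is a count of extra subjects from paring; no paring AE rate is given, and paring is done only where thick scale is present, so any such count would rest on invented inputs.

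**What to change.** 1. In Table 4, make VP-102 the referent of every category, matching the 7.5 text, and record relationship to study procedures such as paring as a separate item.
2. Remove the timing condition from *Unrelated*, so that it applies when there is no known or suspected pattern of response to VP-102 and an alternative cause is present, whatever the timing. It stays distinct from *Possibly related*, which requires a suspected pattern. Making an alternative cause sufficient alone would not do, because the two categories would then overlap. This change places one of the two unfilled temporal combinations. The other, with neither pattern nor alternative cause, stays a matter of judgment, so the site notice should ask for a rating in every case.
3. In SAP 10.2, state that AEs flagged as occurring during paring are shown as procedure-related, and are counted as drug-related only if the investigator attributes them to VP-102. The paring question is already on the AE form.

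The cost is wording in Table 4, an added procedure-relationship item, a sentence in SAP 10.2, a site notice, and a recheck of causality for AEs already recorded. The recheck is the main burden.

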7.6 Expectedness of Serious Adverse Events

An expected AE is one that is consistent with the known risk information described in the product label (if applicable) or the current Investigator's Brochure. The expectedness of an SAE will be assessed by the medical monitor or sponsor on receipt of the initial SAE report.

7.7 Reporting of Serious Adverse Events

Any SAE occurring after the subject signs the informed consent form must be reported to the Sponsor or designee by phone, or e-mail within 24 hours of the time the investigator becomes aware of the SAE (Table 5). Urgent reporting of SAEs is required for the following reasons:

To enable the Sponsor to fulfill the reporting requirements to the appropriate regulatory authority.

To facilitate discussion between the Sponsor and the investigator about appropriate follow-up measures (if necessary).

To facilitate the Sponsor's rapid dissemination of information about AEs to other investigators or sites in a multicenter study.

To facilitate reporting unanticipated problems involving risk to subjects to the IRB.

Table 5 Timeline for Reporting of SAEs

Initial SAE Report		Follow-up SAE Report	
Time Frame	Documents	Time Frame	Documents
24 hours	SAE report	7 days	Updated SAE report

SAE: serious adverse event.

The SAE report must be completed as thoroughly as possible, including the following:

- Subject identification information
- Event term
- All available details about the SAE
- Causality of each SAE
- Signature of the investigator

Within 24 hours of knowledge of a new SAE, the investigative site will enter the event as an SAE into the EDC system being used for this study and recorded into the safety module. The SAE report should include the essential elements.

The SAE report will be forwarded to the Sponsor within the designated time frames. If additional information to complete the SAE report form is needed, the investigator will not wait before notifying the Medical Monitor via the SAE Hotline of the SAE. The SAE report form will be updated by the investigator when additional information is received.

New SAEs, or follow-up SAE information, may be reported to the Research Medical Monitor by calling the SAE Hotline at . The SAE Hotline may be accessed 24 hours/day, 7 days/week. The Hotline is monitored 24 hours/day, 7 days/week. A call to the SAE Hotline is not required and does not alleviate the Investigator of the responsibility to report a new SAE in the EDC system within 24 hours of knowledge.

7.8 Follow-up of Adverse Events and Serious Adverse Events

After the initial AE or SAE report, the investigator is required to follow each subject until the occurrence of one of the following:

The condition resolves and/or stabilizes.

The subject is lost to follow-up.

30-days after the end of study (EOS Visit).

The appropriate SAE report form will be updated in the EDC once the SAE resolves, stabilizes, or is otherwise explained or until the subject is lost to follow-up. The investigator

will also ensure that updates include any supplemental data that may explain causality of the SAE(s).

